1.0 Objectives / Specific Aims

Invasive cervical vagus nerve stimulation (invasive cVNS) is a surgically invasive neuromodulation technique developed in the 1980's to treat intractable epilepsy and chronic refractory major depression[1, 2]. Invasive cVNS involves wrapping a cuff electrode around the left cervical bundle of the vagus nerve and has seen a reemergence in the past decade following several promising animal model findings demonstrating the ability to induce neuroplasticity in a target-dependent manner[3, 4]. In animal models, the temporal pairing of cVNS bursts paired with motor rehabilitation can restore pathologically insufficient neural activity post-stroke [3, 5-7] or correct maladaptive activity in tinnitus[8-10]. This intricate pairing of VNS and restorative behavioral intervention is known as "targeted plasticity" and is a promising approach to treatment of neuropsychiatric interventions, with potentially transformative potential in post stroke rehabilitation. Recently, a noninvasive alternative known as transcutaneous auricular vagus nerve stimulation (taVNS) has emerged as a promising alternative to conventionally implanted cVNS[11-16]. taVNS, however, targets the auricular branch of the vagus nerve, which innervates the human ear and activates the afferent and efferent vagal networks, allowing for a noninvasive, simple, and rapid translation of cervically implanted VNS findings.

Although paired taVNS rehab is promising, there is much work to do before translating this into the clinic. We to refine and develop closed loop taVNS, establish activity with key biomarkers, and show initial feasibility in a small clinical trial. For paired taVNS to succeed as a clinical treatment, it is critical to develop and refine a closed-loop taVNS platform that delivers stimulation concurrently during specific movements of the motor rehabilitation training. Aim 1 develops this novel motion-gated closed-loop system that delivers taVNS in synchrony with specific upper limb motor activation. Aim 2 will combine the development of the closed-loop system with our mechanistic understanding to explore an open-label pilot trial using closed-loop taVNS paired with task-specific training to determine the feasibility, safety, and potential effect size of this novel combination therapy. This work would provide the needed information to move closed loop taVNS into the realm of early phase clinical trials in rehabilitation.

In Aim 2 we propose combining taVNS with protocol-based task-specific training (TST), which is a form of motor rehabilitation therapy that increases the functional use and control of a paretic extremity [17-20]. TST improves functional outcomes and also induces neurophysiological changes in the ipsilesional motor cortex measured by functional neuroimaging and cortical excitability. Combining taVNS with the already established TST may rapidly accelerate and enhance the benefits of TST alone in a targeted neuroplasticity approach.

AIM 1: Establish a motion-activated, closed-loop taVNS platform for post-stroke motor recovery.

Hypothesis: Individualized EMG recording during upper limb rehabilitation is feasible and will generate a robust, specific (<80%), and sensitive (>80%) motion signal to drive taVNS in a safe and automated fashion (n=5).

AIM 2: Determine target engagement and optimal taVNS dosing and effect size of taVNS-paired TST to improve upper limb motor recovery. **Hypothesis:** taVNS delivered to the left ear of chronic stroke patients will activate the vagal afferent network and will induce greater motor cortex BOLD activity in a paired motor task compared to unpaired and placebo stimulation. Pairing closed-loop taVNS with TST induces a targeted cortical neuroplasticity that facilitates the enhancement of TST effects in upper limb hemiparesis in chronic stroke patients. This open label exploratory study will determine safety, feasibility, and effect size to power future controlled trials (n=20).

IRB Number: «ID»

Date Approved «ApprovalDate»

2.0 Background

Nearly 800,000 people in the United States have a stroke annually, with motor impairments being the most common long-term functional disability. 85% of stroke cases result in reductions in upper limb function, and this has a severe negative impact on daily living[21, 22]

Motor recovery is achieved most commonly through professionally assisted motor rehabilitation training, and experimentally through various robotic, virtual reality, and brain stimulation techniques. Many of these rehabilitation techniques attempt to restore pathologically insufficient neural activity post-stroke to regain function, as the stroke induces damage to brain tissue and subsequent reorganization of cortical motor representations in surrounding undamaged tissue [23, 24]. Vagus nerve stimulation (VNS) can enhance motor rehabilitation by increasing neuroplasticity and accelerating the restoration of neural activity and function when paired in a temporally synchronized manner. This proposal aims to develop noninvasive taVNS as an enhancer of neuroplasticity and accelerate motor restoration in post-stroke rehabilitation.

[figure not shown]

Figure 1. VNS-paired shoulder training facilitates cortical plasticity. Adapted from Hays et al, 2013

Underlying basic fundamentals of neuroplasticity is the release of neuromodulators that influence this dynamic neural process. Plasticity may be endogenously influenced (via repeated behavioral training) or exogenously influenced (via noninvasive brain stimulation). One of these exogenous influencers of plasticity is vagus nerve stimulation (VNS), which delivers electricity to the vagus nerve, sending an afferent signal to the brainstem, activating the brain's primary source of norepinephrine (locus coeruleus) which results in broad downstream neuroplastic cellular effects. Lesions to locus coeruleus inhibit this noradrenergic-driven neuroplasticity[25, 26]. VNS is an influencer of neural plasticity and has been paired with various forms of training in animal models to restore deficient or aberrant neural activity[6, 7, 27, 28]. Most notably, rats with implanted VNS electrodes were concurrently stimulated while receiving rehabilitative training post-ischemic stroke induction. 100% of the rats receiving the paired intervention fully recovered forelimb function compared to 22% of rats in the control condition[6, 7].

Cortical reorganization in the VNS group restored pathologically inactive circuits (**Figure 1**). These findings have led to large scale clinical trials (Microtransponder, 2012) exploring the use of VNS-paired rehabilitation to restore upper limb function and are early positive indications of using paired-therapy for rehabilitation. The ongoing invasive cervical clinical trial will report out results in early 2020.

[figure not shown]

Figure 2. taVNS activates the vagal afferent network when compared to sham auricular stimulation. Badran et al. 2018

[figure not shown]
Transcutaneous Auricular Vagus Nerve Stimulation (taVNS) is a Noninvasive Alternative: The auricular branch of the vagus nerve (ABVN) spans from the main bundle of the vagus nerve and innervates the human ear and is the target of a novel form of noninvasive vagus nerve stimulation known as transcutaneous auricular vagus nerve stimulation (taVNS). Modern taVNS was perhaps first described by Ventureyra in 2000[11], with several more recent studies using this novel form of neuromodulation[14, 16, 29-34]. [name] (PI) and the team at the MUSC Brain Stimulation Lab have pioneered several of the early studies demonstrating that taVNS activates the afferent (parasympathetic) vagal system by using cardiac effects as a reliable biomarker to determine optimal stimulation parameters. Following the optimization of the parameter space, [name] conducted a novel concurrent taVNS/fMRI study exploring the direct brain effects of taVNS which revealed activation of the vagal afferent network induced by stimulation of the ABVN[13] (Figure 2).

These data confirm other groups' fMRI findings that taVNS elicits a similar neurophysiological signature as does conventional, implanted VNS. This has led to an emerging new form of brain stimulation – accessed via stimulation of the ABVN, which might enable a non-invasive translation of already FDA-approved invasive treatments for conventional VNS (epilepsy, major depression). This proposal will use taVNS as an inducer of cortical neuroplasticity, pairing taVNS with an already established motor rehabilitation paradigm, and ultimately accelerating the restoration of upper limb function in post-stroke patients. This proposal furthers the already established taVNS paradigm developed by [name] (PI) and allows for the investigation of target engagement of taVNS in a chronic stroke population; refining the method, testing short term biomarkers using fMRI to determine afferent cortical and subcortical activation induced by taVNS, and then showing feasibility in an open label small clinical trial.

4.0 Study Endpoints

This table describes the data collected and the endpoints that will be utilized. The endpoints revolve around clinical assessments (scales administered by a therapist) at weekly increments and at follow-up (2 and 8 week follow-up). These outcomes include Fugl-Meyer Upper Extremity (FM-UE) assessment, Wolf Motor Function Test, Action Research Arm Test, and Motor Activity Log.

There will also be baseline and final kinematic assessments that will be used to track outcomes, however these are secondary measures.

More details about endpoints are described in the study design section.

5.0 Inclusion and Exclusion Criteria/ Study Population

Inclusion Criteria: Subjects must meet the following criteria to participate in this study: 18-80 years old with an ischemic or hemorrhagic stroke that occurred at least 6 months prior; completed conventional rehabilitation therapy at least one month prior; Unilateral limb weakness with Fugl Meyer-Upper Extremity Scale score less than or equal to 58 (out of 66).

All participants must have active wrist flexion/extension and active abduction/extension of thumb.

Exclusion Criteria: Subject who meets any of the following criteria will be excluded from the study: Primary intracerebral hematoma, or subarachnoid hemorrhage; ; Other concomitant neurological disorders affecting upper extremity motor function; Documented history of dementia before or after stroke; Documented history of uncontrolled depression or psychiatric disorder either before or after stroke which could affect their ability to participate in the experiment; Uncontrolled hypertension despite treatment, specifically SBP/DBP>=180/100mmHg at baseline; Contraindicated for MRI scanning.

IRB Number: «ID»
Date Approved «ApprovalDate»

Chronic stroke patients of all ethnic and racial categories will be accepted into this study protocol. No preference will be given based on race, gender or ethnicity. Pregnant females and children under the age of 18 will be excluded for safety reasons. No vulnerable populations or special classes of subjects will be considered for participation.

6.0 Number of Subjects

Specific Aim 1:

Total Planned Enrollment: 5

Specific Aim 2:

Total Planned Enrollment: 20

Chronic stroke patients of all ethnic and racial categories will be accepted into this study protocol. No preference will be given based on race, gender or ethnicity. Pregnant females and children under the age of 18 will be excluded for safety reasons. No vulnerable populations or special classes of subjects will be considered for participation.

7.0 Setting

Aim 1 of the study will be conducted at the MUSC College of Health Professions Building C Rehabilitation Laboratories.

Aim 2 of this study will be conducted both at MUSC [name] (for imaging) and at MUSC College of Health Professions Building C Rehabilitation Laboratories for rehabilitation training.

8.0 Recruitment Methods

Recruitment will be conducted by the study team utilizing the MUSC RESTORE database and MUSC's patient databases via a TriNetX export list to identify and contact prospective chronic stroke patients. A chart review will be conducted for research purposes. Potentially eligible patients will be identified. The potentially eligible patients in the PIs practice will be informed about the study as the PI feels is appropriate. Then potential patients who have agreed to be contacted for future research by logging their MUSC Research Permissions preferences in MyChart will be contacted by phone and invited to participate. All other patients will be contacted through their providers to be informed of the study if the provider feels it is appropriate. Participants will be contacted by any of the IRB approved study personnel and phone screened for eligibility.

9.0 Consent Process

Written informed consent will be obtained from the participant by the PI or designated study team personnel. Consent process will occur remotely via Doxy.me or at the MUSC Center for Health Professions building C (QBAR CORE). Only individuals who pass an initial phone eligibility screening will be eligible to consent remotely or in person.

IRB Number: «ID»

Date Approved «ApprovalDate»

eConsent Process: During an agreed upon time, the ICF/HIPAA form will be reviewed, and all questions will be answered with the potential participant via doxy.me teleconferencing. Once the consent form has been reviewed, the consent is signed in real time by research personnel and the participant. A copy of the signed ICF/HIPAA will be emailed or mailed to the participant.

10.0 Study Design / Methods

Specific Aim 1 – Establish a motion-activated, closed-loop taVNS platform for post-stroke motor recovery (n=5).

[figure not shown]
Prospective participants will be individuals who had a stroke > 6months prior to contact and must meet the following criteria to participate in this study: 18-80 years old with an ischemic or hemorrhagic stroke that occurred at least 6 months prior; completed conventional rehabilitation therapy at least one month prior; Unilateral limb weakness with Fugl Meyer-Upper Extremity Scale score less than or equal to 58 (out of 66).

For more information on tVNS screening please see the uploaded tVNS screening form. Written informed consent will be obtained from all participants prior to participation in the experimental paradigm.

Study Design

Participants will chronic stroke having unilateral limb will be enrolled first into the technology development Aim 1 study (n=5) in which participants will attend a single “mock-TST session”. This session will serve as a closed-loop device optimization study, during which the closed-loop taVNS system will be tested.

Participants will attend one experimental visit (< 1hour) in which we will quantify General Motor Movement of their affected upper limb. We will use large EMG electrodes (Natus Medical, Inc, USA) affixed to 4 major upper limb areas (forearm, bicep, triceps, anterior/mid deltoid), with ground lead attached to ankle. Real-time EMG recording will be conducted using a 4 channel EMG recording system (Motion Lab Systems, Inc) and MATLAB. All EMGS will be event-locked to movement. Retrospective analysis of EMG size will be calculated and used to determine mean and minimum EMG size required for ANY motor movement time-locked to a known movement. The mean minimum EMG size will be used as a prospective threshold level for the motor-gated closed-loop platform used in Aim 2.

EMG Recording

Subjects will be connected to the following devices to measure their muscle activation:

EMG adhesive electrodes (made by Natus Medical) will be adhered to their upper limb in 4 target areas

IRB Number: «ID»
Date Approved «ApprovalDate»

Version 5; Version Date: 12/09/21

(forearm, bicep, tricep, and deltoid). The ground electrode will be attached to the ankle. Electrodes will be connected to a National Instruments DAQ and data recorded and analyzed on MATLAB.

taVNS

Participants will receive taVNS stimulation to their left ear via electrodes attached to the anterior wall of the outer ear canal (25Hz, 500us pulse width, 200% PT). This will not be a therapeutic dose of stimulation, but rather a test of fit, comfort, and closed-loop functionality of the system in development.

We will analyze the EMG data and use it to determine optimal EMG thresholding levels for an automated sensing algorithm to be applied in Aim 2.

This experiment is not intended to provide any benefit to the participant. This serves for a system development and refinement study. All participants in this aim will be able to enroll into Aim 2

Specific Aim 2 – Determine target engagement and optimal taVNS dosing and effect size of taVNS-paired TST to improve upper limb motor recovery (n=20)

Screening

[figure not shown]
Prospective participants will be individuals who had a stroke > 6months prior to contact and must meet the following criteria to participate in this study: 18-80 years old with an ischemic or hemorrhagic stroke that occurred at least 6 months prior; completed conventional rehabilitation therapy at least one month prior; Unilateral limb weakness with Fugl Meyer-Upper Extremity Scale score less than or equal to 58 (out of 66)

For more information on tVNS screening please see the uploaded tVNS screening form. Written informed consent will be obtained from all participants prior to participation in the experimental paradigm.

Study Design

After successful validation of the closed-loop taVNS system is established, Aim 1 participants will be offered the ability to enroll into the Aim 2 & 3 studies of this proposal (n=20), an open-label pilot trial exploring the use of taVNS-paired vs unpaired motor rehabilitation. The primary goal is to determine safety, feasibility, and effect size of this paired therapy.

Participants enrolled in this study will receive upper limb motor rehabilitation (3days/week for 4 weeks. 1 hour/session) by a trained occupational therapist who is part of the college of health

IRB Number: «ID»
Date Approved «ApprovalDate»

professions rehabilitation CORE.

Neuroimaging (baseline and final)

All scanning will be performed on a 3T Siemens TIM Trio (Siemens, Erlangen, Germany). High-resolution T₁-weighted anatomical images will be acquired for each participant. Diffusion kurtosis imaging (DKI) or diffusion tensor imaging (DTI) scans will also be acquired for each participant.

Multiple Interleaved taNS/fMRI scan will be carried out each visit using a gradient echo-based echo-planar imaging (EPI) scan sequence. Biphasic electrical pulses (Current = 200% perceptual threshold; Pulse width = 500µs; Frequency = 25Hz) generated by a Digitimer DS7AH (Digitimer Ltd, Hertfordshire, England) located just outside of the scanner room will be delivered to a special non-ferromagnetic Ag/AgCl clip electrode via a 7-m shielded copper cable. The cable will enter the scanner room through a wave guard. A 100kΩ resister will be placed in series to the stimulating electrode to prevent artificially induced currents from the MRI scanner interacting with the cable and the ear electrodes.

Interleaved taVNS/fMRI pulses will be delivered to the same left tragus or earlobe location as conducted in Aim 1. E-Prime 2 software (Psychological Software Tools, Inc.; Sharpsburg, PA) will be used to trigger a series of tVNS pulses in a block design every 10th TR for exactly 10 TRs (e.g. stimulate during TRs 10-20, 30-40, 50-60, 70-80, 90-100, 110-120) in the scan sequence. A total of 6 interleaved stimulation blocks will be delivered over 8-10 runs. The entire scanning sequence should last less than an hour.

Task-specific training (motor rehabilitation)

All participants enrolled in the pilot dosing trial will receive TST by a trained therapist in the **QBAR CORE**. TST will be administered 3 times per week for 4 weeks (12 total sessions). Each session will last 1 hour, and participants will be connected to EMG electrode arrays that will sense movements while the affected limb is trained in functional tasks like reaching forward to hold a glass and drinking from it, picking up and using objects, fine motor task and dexterity training. During TST, taVNS will be delivered in a movement-gated fashion.

Collected Measures :

MRI: Participants will attend 2, 1-hour fMRI scans (baseline & post-treatment 18) at the MUSC Center of Biomedical Imaging [name] (**Part of the NI Core**). During these neuroimaging sessions, we will collect high resolution T1 structural scans, fMRI BOLD during sequential finger-tapping task (thumb to fifth finger) both paretic and nonparetic hands, followed by the concurrent taVNS/fMRI paradigm (lesioned and contralesional ear targets) developed by [name] here at MUSC.

Clinical Assessments: A therapist from the **QBAR CORE** will conduct weekly clinical assessments on all participants enrolled in this study, including at follow-up visits (2 & 8 weeks post-treatment). Fugl-Meyer Upper Extremity (FM-UE) assessment, Wolf Motor Function Test, Action Research Arm Test, and Motor Activity Log. Assessments will be video recorded and rated by the study's Treatment Occupational Therapist .

Overground Walking: Participants will walk indoors on and off a pressure-sensitive walkway at multiple

IRB Number: «ID»
Date Approved «ApprovalDate»

speeds, but we will not ask them to run or go faster than they feel comfortable and safe. The walkway measures the speed of walking and the size of steps. A physical therapist or trained assistant will walk beside participants across the walkway, and when possible, the participant will be attached to a mobile, ceiling-mounted safety support. They will be asked to walk several times across the walkway.

Treadmill Walking: We will test walking adaptability with a series of tasks. Participants will be asked to walk on a split-belt treadmill at varying speeds, but we will not ask them to run or go faster than they feel comfortable and safe. During all treadmill walking, participants will wear a harness attached to a device attached to the ceiling. This device can move with participants and will catch them and prevent a fall in case of a stumble or misstep. A therapist or trained assistant will stay along to provide any physical assistance participants may need.

Kinematics: Using resources in the **QBAR CORE**, a technician will perform brief kinematic assessments at baseline and immediately following the acute treatment phase of the rehabilitation training on both the affected and unaffected limb. Kinematics of hand and arm will be recorded using a motion capture system with 36 active markers and 10 cameras (PhaseSpace Inc., San Leandro, CA). We will capture movement during three specific tasks (reach, grasp, single joint movement) and quantify functional improvements comparing post-treatment kinematics to baseline as well as between affected and unaffected limbs.

Daily Life Activity Improvement Using Actigraphy: At-home upper limb motor activity of both the paretic and nonparetic limb will be collected using 2 independent actigraphy monitors (ActiGraph, Pensacola, FL), one on each arm, during the treatment phase of this trial. We will assess overall activity of upper limbs, as well as the ratio of activity of the paretic vs non-paretic arms.

Estimated Difficulties, Limitations and Time Frames

Estimated Difficulties. Many of the potential problems will manifest in the development of determining optimal EMG Quantification thresholding in chronic stroke patients in AIM 1. Although our lab is very experienced and we have resolved this type of scientific problem in the past with the administration of closed-loop TMS in the Brain Stimulation Lab.

Limitations. There are two potential limitations with these studies. The first is tolerability of electrical nerve stimulation of the tragus and earlobe. Although we do not anticipate any issues, drop-out may be an issue due to discomfort of the stimulation. If discomfort occurs we will decrease stimulating current amperage.

Estimated Time Frames. We plan on completing Aim 1 within 3 months. Specific Aim 2 will take approximately 18 months to complete (20 individuals attending rehabilitation training programs, with about 3 participants recruited every 3 months).

	Treatment Day					F/U Week	
	0	3	6	9	12	2	8
MRI	X				X		
Clinical Assessment	X	X	X	X	X	X	X
Kinematics	X				X		
Take-Home Actigraphy	Utilized During Treatment Phase					X	X

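### The Aim 2 movement trigger is taken from a mean minimum EMG size in five Aim 1 participants, with no calibration to the Aim 2 participant described, so sensitivity above 80% is not assured in people with weak signals.

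*Protocol*

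**What the plan says.** The Aim 1 hypothesis in Section 1.0 begins "Individualized EMG recording during upper limb rehabilitation is feasible" and sets a sensitivity target above 80% for the motion signal that drives stimulation.

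Section 10.0 describes how the trigger is obtained. Participants are "enrolled first into the technology development Aim 1 study (n=5) in which participants will attend a single" mock training session of under an hour. Electrodes are "affixed to 4 major upper limb areas (forearm, bicep, triceps, anterior/mid deltoid"). A retrospective analysis of EMG size is "used to determine mean and minimum EMG size required for ANY motor movement time-locked to a known movement". The operative sentence follows: "The mean minimum EMG size will be used as a prospective threshold level for the motor-gated closed-loop platform used in Aim 2". Shortly afterwards the same section says the Aim 1 data will be used to "determine optimal EMG thresholding levels for an automated sensing algorithm to be applied in Aim 2", with levels in the plural.

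The Aim 2 account of task-specific training says that EMG arrays sense movement and that stimulation is gated by it. It describes no calibration by participant, channel or session. Aim 1 participants may continue: "All participants in this aim will be able to enroll into Aim 2".

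Three other places bear on this. Section 3.0 says timing is critical and stimulation must be precisely synchronized with training. Section 5.0 admits FM-UE scores of 58 or less with no lower score limit, but requires active wrist and thumb movement. Section 13.0 makes the start of Aim 2 conditional on DSMB review of the Aim 1 data.

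**The concern.** EMG size can be expected to differ between people, muscles and electrode placements. A threshold at the mean of several people's minima lies above the minimum of anyone whose signal is weaker than that average. Such a participant may make true movements that do not reach the trigger, while someone with a strong signal loses almost none. Followed as written, the rule has nothing that scales it to the individual.

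The stake is the estimate that Aim 2 exists to produce. Section 12.0 plans 20 participants, 10 per cell, to obtain effect sizes for a follow-up proposal. If the number of paired stimulations depends on signal strength, the estimate mixes the effect of pairing with failures of the trigger. Ten per cell is too few to separate the two afterwards.

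**Working it through.** **The plan's own figure.** The sensitivity target above 80% is a hypothesis. It cannot be reproduced, because the protocol gives no EMG amplitudes, spreads or number of movements. What follows is a sensitivity analysis on assumptions.

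**Inputs from the protocol.** Five Aim 1 participants, one session each; threshold equal to the mean minimum EMG size; four recording areas; sensitivity target 80%; 20 participants in Aim 2.

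**Assumptions.** Movement amplitude is log-normal, with between-person log-SD sb and within-person log-SD sw. Each Aim 1 participant makes m = 40 known movements. The mean is taken over the five personal minima, giving T.

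**Formula, one channel.** A new person with log level b has sensitivity Φ((b − ln T)/sw). This is below 80% when b < ln T + 0.84·sw.

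**Hand check at sb = 0.5, sw = 0.3.**
- The expected minimum of 40 standard normals is about −2.16, with variance about 0.2. A personal log minimum therefore averages −2.16 × 0.3 = −0.648, with variance 0.25 + 0.2 × 0.09 ≈ 0.268.
- The mean of one minimum on the raw scale has log −0.648 + 0.268/2 ≈ −0.514.
- For a mean of five, the squared coefficient of variation is (e^0.268 − 1)/5 ≈ 0.061, so ln T centres near −0.514 − 0.061/2 ≈ −0.545.
- The 80% limit is −0.545 + 0.84 × 0.3 ≈ −0.293. The SD of b − ln T is √(0.25 + 0.061) ≈ 0.557.
- The share below 80% is Φ(−0.293/0.557) = Φ(−0.526) ≈ 30%, which agrees with the simulation.

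**Simulation, share of new participants below 80% sensitivity.** The four-channel column assumes one threshold per channel, a trigger when any channel crosses it, every movement active in all four channels, correlation of personal levels between channels 0.5 to 0.8, and within-person correlation 0.5.

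| sb | sw | One channel | Four channels, any trigger |
|---|---|---|---|
| 0.3 | 0.3 | 15% | 0–2% |
| 0.3 | 0.5 | 4% | 0% |
| 0.5 | 0.3 | 30% | 5–11% |
| 0.5 | 0.5 | 17% | 1–2% |
| 0.7 | 0.3 | 39% | 11–19% |
| 0.7 | 0.5 | 28% | 3–8% |
| 1.0 | 0.3 | 49% | 17–28% |
| 1.0 | 0.5 | 40% | 10–18% |

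Runs differ by about a percentage point, so the ranges for sb 0.5 to 1.0 are quoted as about 16–49% and 1–29%.

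**Wider one-channel ranges (m 10 to 100, sw 0.3 to 0.7).** With sb = 0, mean sensitivity is 92–99% and under 1% of participants fall below 80%. With sb = 0.25 the share is 0–27%; with 0.5, 4–43%; with 1.0, 25–56%.

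**Overlap of the aims.** If all five Aim 1 participants are among the 20, the one-channel shares change by at most about 1.5 percentage points (for example, 30% becomes 29%).

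**The case against.** There is a good case that the problem is smaller than it looks.

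- **The averaging is not defined.** The text does not say whether the mean is over people, movements or muscles, and it also speaks of levels in the plural. A reader might infer a single cut-off for all muscles, but the protocol does not fix that. This stands. A separate level for each muscle would still not be scaled to the person.
- **The threshold need not come from other people.** Aim 1 participants may enter Aim 2, so up to 5 of the 20 could have contributed to it. This stands but hardly changes the result.
- **There is no literal contradiction.** In the hypothesis, the word individualized describes the recording, not the threshold. The two statements are in tension and no more.
- **A mean minimum is lenient by construction.** With little between-person spread, sensitivity stays above 90%. Four channels with an any-channel trigger cut the loss sharply, and the protocol is as compatible with that model as with one channel. A reader might infer that many movements will be missed; the documents support only that they may be.
- **Missed pairing need not follow impairment.** That inference requires a link between EMG size and FM-UE that the protocol never gives, and eligibility requires some active wrist and thumb movement.
- **There are gates before Aim 2.** The system must be validated and the DSMB must approve. In the one-channel scenarios with sb 0.5 to 1.0, at least one of the five Aim 1 participants falls below 80% in about 48% to 98% of replicates, so Aim 1 would often expose the problem. It would not always do so, and the protocol does not say that sensitivity will be judged person by person or on movements that did not set the threshold.

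A comparison with a personal cut-off also proves little on sensitivity alone. A threshold at a person's own 5th percentile gives about 95% by definition, and false triggers were counted for neither rule.

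**Conclusion.** The point holds as a weakness in a stated design rule and should be corrected. The protocol carries a mean minimum EMG size from a five-person, single-session sample into Aim 2 and describes no calibration there. Such a value cannot assure the hypothesized sensitivity in weak-signal participants.

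The direction is secure; the size is not. It rests on assumed log-normal amplitudes, on the mean being taken over people, and on how the channels are combined. The assumed ranges run from a negligible loss to about half of participants below 80%, so no single figure should be quoted as the expected miss rate.

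The consequence for the trial is that delivered pairing may vary with signal strength and blur the effect-size estimate. Confounding with baseline severity is possible but is not shown by the documents.

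**What to change.** Reconcile Section 1.0 (Aim 1 hypothesis) with the Aim 1 and Aim 2 parts of Section 10.0, so that Aim 1 fixes the signal-detection rule rather than a pooled value. State what the rule averages over and how the four channels combine. Derive the Aim 2 detection threshold from each participant's own EMG, in a brief block of cued movement and rest with the electrodes already applied for the session.

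In Aim 1, check the rule on movements not used to set it, for example by calibrating on the first half of the mock session and scoring the second half. Report missed movements and false triggers for each participant.

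The cost is protocol wording and a few minutes of session time, with no new equipment. This concerns signal detection only; no threshold value or stimulation dose is proposed.
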